Protocol Title: User-Led Meaningful Activity and Early-Stage Dementia

Document Title: Study Protocol

NCT: NCT05159869

Document Date: 03DEC2021

Study Protocol

The clinical trial phase will be a pilot randomized, controlled trial exploring the design and feasibility of a novel approach to dementia intervention development. The randomized, controlled pilot study compares the efficacy of the co-creation of a tailored activity plan with a wait-list control group. Using a two-group randomized, parallel design, 60 persons with early-stage dementia will be assigned to treatment or wait-list control.

Recruitment: Potential participants will be recruited through 1) the Johns Hopkins University Maximizing Independence (MIND) at Home study, 2) the Johns Hopkins Bayview Medical Center Memory Clinic, 3) community-based social agencies such as the Alzheimer's Association, and 4) independent and semi-independent residences designed for older adults including continuing care retirement communities and assisted living facilities. Recruitment efforts are aimed at persons living with early-stage dementia and their informal/unpaid caregivers using three main forms of messaging: (a) flyers, (b) a description of the study that was prepared originally for clinicaltrials.gov, and (c) in-person recruitment presentations. All recruitment materials describe the general nature and goals of the research and provide information about what participation involves and monetary compensation. The Principal Investigator (PI) is listed as the source for additional information and addressing questions in all materials.

Pre-Screening: Contact with potential participants will primarily be made through the potential participant contacting the study phone number on advertisements or speaking with the PI following recruitment presentations. Interested persons who believe they have early-stage dementia must: 1) be English-speaking, 2) be medically stable and responsive to the environment (e.g., not comatose), and 3) have a designated caregiver or care partner who lives within close proximity or resides with them. If potential participants with dementia are on any of four classes of psychotropic medications (antidepressant, benzodiazepines, antipsychotic, or anti-convulsant) or an anti-dementia medication (memantine or a cholinesterase inhibitor), it is required that he/she be on a stable dose for 60 days prior to enrollment (typical time frame in clinical trials) to minimize possible confounding effects of concomitant medications. Individuals are excluded if: 1) they are bed-bound, defined as confined to bed or chair for at least 22 hours a day for at least four of the previous seven days, 2) are receiving palliative care or are at end-of-life, 3) have schizophrenia or a bipolar disorder, 4) their cognitive decline is secondary to probable head trauma, or 5) they are taking any neuroleptic medications or have any of the following medical diagnosis: (a) restless legs syndrome, (b) delirium, or (c) akathisia, medication-induced, or other movement disorders such as Parkinson's disease or essential tremor. The primary criteria for inclusion in the study is a diagnosis of early-stage dementia, but this is not ascertained during pre-screening as it is contingent on the results of baseline neuropsychological assessment as described below.

Consent: For those identified as potentially eligible at during pre-screening, the PI will obtain informed consent in-person immediately prior to the neuropsychological

assessment. For caregiver and PLWD interviews, the PI introduces herself, explains the study purpose and procedures and reviews the Johns Hopkins University IRB approved informed consent. Informed consent guidelines of the Johns Hopkins University's Review Board will be followed. The informed consent details the study objectives, procedures, steps to maintain confidentiality, and the risks and benefits of this study and will be presented to each participant and their caregiver in their home. The informed consent procedure will emphasize that participation is strictly voluntary and may be withdrawn at any time.

Participant Remuneration: Participants will be compensated for their time based on length of study participation, and all persons who complete the baseline neuropsychological assessment will receive a minimum of \$100. The maximum amount of remuneration is \$500 at the 12-month, final data collection time point.

Baseline Assessment and Screening Procedures: Following in-person informed consent, all potential participants will undergo in-person neuropsychological testing prior to randomization in order to establish baseline cognitive functioning and verify that they are indeed in the early stages of dementia (i.e., "mild" dementia). This testing will take approximately two hours and will be administered and scored/interpreted by the PI, who previously received extensive training in neuropsychological assessment, interpretation, and feedback. Cognitive domains evaluated will include global cognitive status, learning and memory, attention, processing speed, executive function, visuospatial skills, and language. If test results indicate that a participant has early-stage dementia, he or she will then be randomly assigned to the intervention group or wait-list control. For those individuals who meet criteria, assessments measuring aspects of well-being, sense of self, sense of control, and frequency/severity of neuropsychiatric symptoms will also be administered. Specifically, various subtests from the following protocols will be used: Test of Premorbid Function, Wechsler Memory Scale-III, Wechsler Adult Intelligence Scale-Fourth Edition, Trail-Making Test Parts A and B, Stroop Color-Word Test, Controlled Oral Word Association Test, Boston Naming Test, Rey-Osterrieth Complex Figure Test, and Repeatable Battery for the Assessment of Neuropsychological Status. The purpose of the home clinical assessment is to confirm dementia diagnosis and staging, review medication use, and exclude delirium and other conditions as described above. The Neuropsychiatric Inventory, Geriatric Depression Scale, Geriatric Anxiety Inventory, MIDI Sense of Control Scale, Wallhagen Perceived Control Questionnaire, Identity-Alzheimer Moderate Test, and IMAGE Test will also be administered.

Feedback Session: The potential participant and his/her caregiver will be provided with feedback from the neuropsychological assessment within one week of testing. If the results indicate that the potential participant is cognitively healthy, meets criteria for mild cognitive impairment, or meets criteria for dementia that has advanced beyond the early, or mild, stage, this will be the final session with the potential participant. If the results of the assessment indicate that the potential participant is indeed at a mild stage of dementia, he or she and the PI will work together in a subsequent session to co-design a meaningful activity plan and map out a gradation plan to correspond with

disease progression. The caregiver will be advised on how to modify/grade the activity(ies) as the disease advances.

Randomization and Study Arm Protocol: Persons randomized to the User-Led Meaningful Activity intervention group will begin the treatment protocol (described below) right after randomization. The intervention will consist of 2-3 sessions lasting 60-90 minutes each in which participants identify the basis/topic of the activity plan, receive dementia psychoeducation, and map out an activity gradation plan. There will be a check-in at 8 months. The neuropsychological battery that was administered at baseline will be re-administered 4 months and 12 months after baseline. Persons randomized to the wait-list control group will begin the treatment protocol after four months' time. There will be a check-in at 8 months. The neuropsychological battery that was administered at baseline will be administered 4 months and 12 months after baseline.

Co-Design of Meaningful Activity Plan: The *first co-design session* will involve an assessment of the person living with dementia's (PLWD) interests, values, and cherished "roles" (e.g., position at work, role within the family, hobby) using a range of performance based and self-report elicitation methods. The goal of this session is to identify 1-3 important interests, hobbies, or roles that the person with dementia is concerned about losing or disconnecting from as the disease progresses. While, ideally, the identification of this interest, hobby, or role should come directly from the participant, it is possible that some participants may need prompts or suggestions. If necessary, the Activity Card Sort will be used to facilitate the discussion of participant interests and valued roles, which will also be informed by principles from studies examining the values and preferences of PLWD as they relate to care. Development of the activity plan may take more than one session.

During the *second co-design session*, the completed meaningful activity plan will be reviewed with the PLWD and their caregiver and modified if necessary. The 1-3 meaningful activities identified in the first session will have an associated gradation plan to accommodate disease progression. An example gradation plan, based on the PI's work with participants in the Treatment Routes for Exploring Agitation (TREA; PI: [name]) study, is as follows: (1) an individual who is/was a researcher may continue to maintain a job, conduct research, and even publish papers in the early stages of dementia. (2) As the dementia progresses, the nature of the person with dementia's relationship to the research will likely change. He or she may be able to continue to run analyses and read/access literature in his or her field. (3) In the moderate stages of dementia, this participant may read his or her existing publications or go to museums showcasing research of interest. As the disease approaches the severe stage, the participant may read very basic books about his or her former profession. (4) In the severe stages of dementia, this study participant may watch videos related to the former profession, e.g., BBC or National Geographic.

In the *final session* with the PLWD and his or her caregiver, the PI will provide psychoeducation on the stages of dementia. This is designed to help the caregiver recognize signs of progression, and prepare the PLWD for greater involvement of the

caregiver as the dementia progresses. This session will also involve a discussion of how to modify the activity and follow the gradation plan through the stages of dementia. Carer participation is essential for the delivery and sustainability of the intervention, as the PLWD will have increasing difficulty with activity initiation over time.

Study Reminders: The PI and study staff will contact study participants monthly via phone to inquire about how the implementation of the meaningful activity plan is going, answer any questions, and elicit feedback related to intervention feasibility and acceptability. For persons in the wait-list control group, these phone check-ins will also occur each month during the four months prior to co-design and intervention implementation, but the focus will be reminding them of their start-date and that they are still enrolled in the study and study staff are looking forward to working with them.

Follow-Up Data Collection Periods: Treatment group participants will receive the intervention, and will be reassessed at 4 months and 12 months from baseline. There will also be a "check-in" after 8 months' time. Four months after their baseline, wait-list controls will receive the same intervention and will be reassessed, and again at 12 months from baseline. There will be an 8-month visit for wait-list controls. This design allows for estimation of effect sizes using a randomized two-group design at four months, confirmation of treatment gains for wait-listed participants from 4-12 months, and evaluation of intervention acceptability.

Feasibility and Acceptability: Feasibility and acceptability as perceived by the PLWD and the caregiver will be assessed through semi-structured interviews and rating scales. Regarding rating scales, the PLWD and caregiver will separately be asked to rate intervention feasibility and acceptability using the following questions on a three-point Likert scale (1 = not at all, 2 = somewhat, 3 = very): 1) Was the meaningful activity plan useful? 2) How easy was it to incorporate the activities into your routine? 3) How easy was it to follow the instructions for adjusting the activities if needed? 4) Did the meaningful activity plan increase the amount you did enjoyable activities? 5) How satisfied were you with the meaningful activity plan? 6) Was participation in this study burdensome? 7) Do you think you will continue using the activity plan now that you are done with the study?

In addition to these seven questions, the caregiver will be asked to rate the following on the same Likert scale: 1) Did this meaningful activity plan relieve any caregiving-related stress? 2) Were there any insurmountable barriers to incorporating these activities into your care recipient's routine? 3) Did participation in this study positively impact your relationship with your care recipient?

Feedback from the semi-structured interviews and follow-up questions in response to the rating scale responses will be evaluated and used in concert to capture the multidimensional aspects of feasibility and acceptability.

Protocol Title: User-Led Meaningful Activity and Early-Stage Dementia

Document Title: Statistical Analysis Plan

NCT: NCT05159869

Document Date: 21AUG2025

Statistical Analysis Plan

The study followed a randomized, two-arm parallel design. Seventy (70) dyads comprising community-dwelling individuals with early-stage dementia and their primary caregivers were assigned to treatment or wait-list control. Treatment group participants received the co-designed meaningful activity intervention, and all dyads were reassessed at four months from baseline. After four months, wait-list control dyads received the same intervention and were retested four months later (i.e., eight months from baseline).

Analyses were based on the Intent-To-Treat (ITT) principle, including every patient who was randomized. All tests were performed at two-tailed significance $\alpha=0.05$. First, chi-squared and t-test tests were used to compare intervention and control dyads on baseline characteristics. The primary hypothesis held that a co-designed meaningful activity intervention would significantly decrease the frequency and intensity of neuropsychiatric symptoms (NPS) and slow cognitive decline across multiple domains (i.e., memory and learning, executive function, visuospatial abilities, attention, language, processing speed). The secondary hypothesis was that a co-designed meaningful activity intervention would significantly increase emotional well-being (e.g., reduce depression and anxiety) and strengthen self-identity. To test the hypotheses, main treatment effects at four months were examined using analysis of covariance (ANCOVA). Given prior research linking caregiver characteristics to ratings of neuropsychiatric and psychosocial outcomes, caregiver sex, race/ethnicity, education, and relationship to the person living with dementia (PLWD) were identified a priori as covariates. Standardized effect sizes (d) were calculated as the adjusted mean difference between groups divided by the square root of the model's mean square error (MSE).

To evaluate whether wait-list control participants derived benefits comparable to those of the meaningful activity group after receiving the intervention, change scores were examined from 4 months (T2) to 8 months (T3) in the wait-list control group and compared with change scores from baseline (T1) to 4 months (T2) in the meaningful activity intervention group. Analyses were conducted using the same ANCOVA framework applied in the primary analysis. It was hypothesized that the magnitude of treatment effects would be similar across groups, reflecting replication of benefit, and therefore the between-group difference in change would not be statistically significant.

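### The SAP claims ITT with every randomized patient, but gives no handling of missing values and lists no baseline outcome score in the four-month ANCOVA

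*SAP*

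**What the plan says.** The SAP's design paragraph reports that "Seventy (70) dyads comprising community-dwelling individuals with early-stage dementia and their primary caregivers were assigned to treatment or wait-list control" and that "all dyads were reassessed at four months from baseline". For the wait-list arm it reports a retest at eight months, but does not say that all of those dyads were retested.

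The analysis paragraph then states: "Analyses were based on the Intent-To-Treat (ITT) principle, including every patient who was randomized". Of the hypotheses it says that "main treatment effects at four months were examined using analysis of covariance (ANCOVA". On adjustment it says that "caregiver sex, race/ethnicity, education, and relationship to the person living with dementia (PLWD) were identified a priori as covariates". The baseline value of the outcome is not in that list.

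In the SAP's last paragraph, "change scores were examined from 4 months (T2) to 8 months (T3) in the wait-list control group"; these are compared with baseline-to-four-month change in the intervention arm, using the same ANCOVA framework.

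Neither document names an imputation method, a likelihood-based repeated-measures model, a missing-data assumption or a sensitivity analysis. Neither gives the number of dyads analysed for any outcome.

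**The concern.** A standard ANCOVA without imputation drops every record that lacks the outcome or a covariate. The claim that all randomized patients are included is therefore true only where nothing is missing, and the plan offers no method for the other case.

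Gaps can arise in several ways. The Protocol's consent section lets participants withdraw at any point. The neuropsychological battery takes about two hours and is repeated in people with dementia, so a dyad can be seen without completing every test. Each of the four caregiver covariates is another way to lose a record.

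The eight-month comparison is more exposed. The wait-list arm needs two post-baseline scores, the intervention arm only one. The Protocol schedules the battery at 4 and 12 months and only a check-in at 8. The SAP predicts a non-significant difference there, so lost records make the predicted result easier to obtain.

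If loss is related to severity and differs by arm, a model without the baseline score compares groups that are no longer balanced, under an ITT label.

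**Working it through.** **Inputs from the documents.** 70 dyads randomized (SAP; split by arm not given), two-sided alpha 0.05 (SAP), ANCOVA at four months with caregiver covariates (SAP). The documents give no power, effect size, SD or loss rate, so there is no plan figure to reproduce.

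**Assumptions.** 35 dyads per arm, SD 1, loss of 0-30%, correlation between baseline and four-month score (rho) of 0.5-0.7, and 80% as a reference power.

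**Step 1: is a mismatch shown?** Read literally, complete reassessment at four months gives an ANCOVA set of 70 of 70, equal to the ITT set, provided that every outcome and covariate was recorded. No dyad without a four-month value is documented. There is no such statement for eight months.

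**Step 2: what loss would cost in precision.** Number analysed = 70 × (1 − loss). Detectable d is from the noncentral t distribution with n per arm, 80% power and no covariate gain.

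| Loss | Dyads analysed | n per arm | Detectable d |
|---|---|---|---|
| 0% | 70 | 35 | 0.68 |
| 10% | 63 | 31.5 | 0.72 |
| 20% | 56 | 28 | 0.76 |
| 30% | 49 | 24.5 | 0.82 |

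The normal approximation, (1.960 + 0.842) × √(2/n), gives 0.67 at n = 35 and 0.80 at n = 24.5.

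**Step 3: bias if loss is related to baseline.** Simulation with 6,000 runs, 35 per arm and no true effect. Treated-arm loss rises with baseline severity (log-odds 1 per SD); wait-list loss is random at the same overall rate. Caregiver covariates are left out.

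| Loss | False benefit without baseline, rho 0.5 | Same, rho 0.7 |
|---|---|---|
| 10% | 0.042 SD | 0.064 SD |
| 20% | 0.091 SD | 0.120 SD |
| 30% | 0.125 SD | 0.174 SD |

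Rejection under the null was 5.1-9.4% without baseline. With the baseline score in the model, absolute bias was below 0.005 SD and rejection was 4.8-5.2%. Repeat runs gave 0.04-0.18 SD and up to 9.7% without baseline, and at most 0.007 SD with it, within simulation error.

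Rough check: the shift in one arm's mean = fraction missing × (difference between missing and observed dyads). With a 0.5 SD difference, this is 0.10 × 0.5 = 0.05, 0.20 × 0.5 = 0.10 and 0.30 × 0.5 = 0.15 SD, the same order as the table.

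**Step 4: would a longitudinal model restore the full set?** Take a model of baseline and four-month scores with a common baseline mean and unstructured covariance, fitted by REML without caregiver covariates. Its four-month effect matched the complete-case, baseline-adjusted ANCOVA to below 1e-7, and the standard errors differed by 2-3%. Dyads without a four-month score enter the model but do not move the estimate. The gain in Step 3 therefore comes from using the baseline score.

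**Step 5: complete data.** Adjusting for baseline multiplies the standard error by about √(1 − rho²). This is √0.75 = 0.866 at rho 0.5 (13.4% smaller) and √0.51 = 0.714 at rho 0.7 (28.6% smaller). With 70 dyads and one more coefficient to estimate, the reductions are about 13% and 28%.

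**The case against.** A reader might infer that the analysis delivered was not ITT. The documents do not support that. The SAP is written in the past tense and reports reassessment of all dyads at four months. If every measure was completed, the claim is true at that time point. What is shown is an unstated rule, not a dropped dyad.

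The size is also open to challenge. The 10-30% loss is assumed, while the text read literally implies no missed visits at four months. The bias scenario puts severity-related loss in one arm only, and swapping the arms reverses the sign. The bias arises from leaving out the baseline score, since complete-case data analysed with it show none. A longitudinal model would not recover most of the lost power, and a missing caregiver covariate would still drop a dyad from it.

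The term ANCOVA often implies a baseline covariate, so the score may have been used and not listed. In that case the bias and precision points fall away, and the reporting gap remains.

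All of this stands as a limit on the claim. Attendance is not completion of every scale, however, and nothing is said about completeness at eight months. The eight-month comparison sets different periods in the two arms against each other. It is not a same-period randomized contrast, so the argument about lost randomization applies to the four-month analysis only.

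**Conclusion.** The point holds conditionally. The ITT claim may be correct at four months, but no stated method backs it for any outcome or covariate with missing values, or for the eight-month analysis. The reader cannot verify the number analysed.

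Under the stated assumptions, the ANCOVA as listed is biased by about 0.04-0.18 SD, and false positives reach nearly 10% in the worst case. At 10% loss the bias is small. Leaving out the baseline score also forgoes a 13-28% smaller standard error at rho 0.5-0.7, whether or not anything is missing. The simulation covers only loss that depends on baseline; it says nothing about loss that depends on the unseen four-month score. This is worth changing, but it does not by itself invalidate the trial's results.

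**What to change.** - Put the baseline value of each outcome in its four-month model and keep the caregiver covariates. An ANCOVA covariate or a constrained longitudinal model will do; with two time points they give essentially the same effect. Because the SAP describes analyses already done, show the result beside that of the model as listed.
- Report the number analysed per outcome and arm at four and eight months. If it is 70 of 70 for every outcome at four months, one sentence settles the ITT claim there.
- If any value is missing, call the ANCOVA complete-case and drop the claim that every randomized patient is included. Add one delta-adjusted multiple-imputation sensitivity analysis that covers missing covariates and, for the replication comparison, the eight-month scores.

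The cost is modest re-analysis of data already held, with no new collection. It repeats over about 11 outcomes: neuropsychiatric frequency and intensity (2), cognitive domains (6), depression and anxiety (2), self-identity (1). The baseline-adjusted analysis relies on data being missing at random, which the delta adjustment probes.

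### The SAP tests a multi-part primary hypothesis with every test at two-sided 0.05, and gives no success rule, composite, testing order or multiplicity adjustment

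*SAP*

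**What the plan says.** The SAP, in the paragraph that sets out the hypotheses, states a single primary hypothesis: the intervention "would significantly decrease the frequency and intensity of neuropsychiatric symptoms (NPS) and slow cognitive decline across multiple domains". The domains follow in parentheses: "memory and learning, executive function, visuospatial abilities, attention, language, processing speed". The same paragraph says "All tests were performed at two-tailed significance" 0.05, and that the hypotheses are tested by ANCOVA on the four-month treatment effect. For effect sizes it says "Standardized effect sizes (d) were calculated as the adjusted mean difference between groups" over the root mean square error.

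The SAP assigns no score to any domain. In the protocol, the section on baseline assessment and screening lists nine cognitive test protocols and says "various subtests from the following protocols will be used". It does not say which subtests represent which domain, or how many.

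On purpose, the protocol's opening paragraph calls the trial a pilot of design and feasibility, and then says "The randomized, controlled pilot study compares the efficacy of the co-creation of a tailored activity plan with a wait-list control group". Its section on follow-up data collection says that the design permits effect sizes to be estimated at four months.

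Neither document names one primary endpoint, a composite or global test, an order of testing, a multiplicity adjustment, or the number of components that must be significant for the hypothesis to count as supported.

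**The concern.** A reader of the results cannot tell which pattern of findings would support the primary hypothesis. Suppose that one domain reaches p < 0.05 and the rest do not. The SAP neither allows nor forbids reporting this as support. The false favourable rate of such a claim depends on a rule that is not written down: it is no more than 2.5% if all components are needed, and several times that if any one is enough.

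The timing adds to the difficulty. The SAP is dated 21 August 2025 and describes the analyses in the past tense, so a rule supplied now may be supplied with the results in view. At stake is whether a statement that the primary hypothesis was supported can be interpreted. The individual four-month estimates are not affected.

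**Working it through.** The documents give no power calculation and no family-wise error rate, so there is no stated figure to reproduce.

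**Inputs from the documents**
- Significance level: two-sided 0.05 for all tests, so 0.025 in the favourable direction (SAP).
- Outcomes: six named cognitive domains plus NPS. This gives 6 + 1 = 7 if frequency and intensity form one score, or 6 + 2 = 8 if they are separate (SAP).
- Sample size: 70 dyads, with no allocation ratio (SAP). It is used only for the simulation check and the cost of adjustment.

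**Assumptions**
- One test per domain. The SAP implies this but does not say it.
- A common correlation rho between test statistics, from 0 to 0.9. The documents give none.
- All treatment effects null.
- Where a sample size is needed: 35 per arm, complete data and an unadjusted two-sample t-test.

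**Step 1. Any one significant outcome counts, rho = 0.** The chance of at least one false favourable result among k tests is 1 − (1 − 0.025)^k.
- k = 7: 1 − 0.975^7 = 16.2%
- k = 8: 1 − 0.975^8 = 18.3%

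**Step 2. The same rule with correlated outcomes.** For equicorrelated normal statistics the chance is 1 − ∫ φ(u) Φ[(1.96 − √rho·u)/√(1 − rho)]^k du. The row for 12 tests only illustrates several subtests per domain; the documents give no such count.

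| Tests | rho 0 | 0.3 | 0.5 | 0.7 | 0.8 | 0.9 |
|---|---|---|---|---|---|---|
| 7 | 16.2% | 13.7% | 11.5% | 8.9% | 7.4% | 5.7% |
| 8 | 18.3% | 15.2% | 12.5% | 9.5% | 7.9% | 6.0% |
| 12 | 26.2% | 20.2% | 16.0% | 11.6% | 9.3% | 6.7% |

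The comparison for a single test is 2.5%. Simulated t-tests with 35 per arm (200,000 runs per setting) agree: 16.1% and 9.0% for seven outcomes at rho 0 and 0.7, and 18.4% and 9.6% for eight.

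**Step 3. Every component required.** The rate cannot exceed 2.5%. That bound is reached when one component is null and the others have large effects. With all effects null and rho up to 0.9, it is at most 0.7%.

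**Step 4. Holm adjustment at family-wise 0.05.** With all effects null, the false favourable rate for seven or eight outcomes is about 1.5% to 2.5% at rho 0 to 0.7, and about 1% at 0.9 (400,000 draws).

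**Step 5. Cost of Holm.** The first step across eight scores tests at 0.05/8 = 0.00625. The difference detectable with 80% power (noncentral t, 35 per arm) rises from 0.679 to 0.879 SD.

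**The case against.** The strongest reply is that the hypothesis is a conjunction. Read plainly, NPS and cognition must both improve, and if all components are needed there is no inflation. This is a fair reading and may be what was meant. But the SAP never turns the sentence into a decision rule, and the wording does not settle whether all six domains, or only some, must improve. If every component was meant, that also needs stating because it is demanding. With a true effect of 0.68 SD in each of eight outcomes (35 per arm, complete data, t-tests), power would be 17% at correlation 0 and 52% at 0.7, against 80% for one test.

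A second reply is that this is a pilot meant to estimate effect sizes, where formal error control is partly a matter of judgement. That lowers the weight of the point. It does not remove it, because the protocol also speaks of comparing efficacy, and the SAP poses a primary hypothesis of significant effects at 0.05 without calling the tests exploratory.

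A third reply is that the count of seven or eight is inferred, since the SAP does not say that each domain has its own ANCOVA. This stands, and the count is treated here as an assumption. Several subtests per domain would raise the rate; a single cognitive composite would lower it, but none is described.

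A reader might infer that the plan has a false positive rate of up to 18%, or that the rule was left open on purpose. The documents support neither. The percentages belong to one possible rule that the SAP does not adopt, and past-tense wording shows when the text was written, not how any choice was made.

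**Conclusion.** The point holds as a gap in the decision rule that leaves claims based on individual significant outcomes without error control. That gap is plain in the text and depends on no calculation.

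Its size is conditional. It is about 6% to 18% against 2.5% if all of the following apply: each domain is tested separately, any one significant outcome is taken as support, there are seven or eight outcomes, all effects are null, and the correlation lies between 0.9 and 0. If every component is required, the rate is at most 2.5%. The SAP does not say which rule applies. This should be corrected in the SAP and the report, but the trial remains interpretable as a study that estimates effects.

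**What to change.** Use the existing data, and date the change as made after the analysis.

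1. Report every primary outcome that was analysed, with its four-month estimate and 95% CI. State whether NPS is one score or two, and list the scores used for each domain.
2. Then do one of the following:
   - Label the four-month primary results exploratory and make no significance claims. This fits a pilot that aims to estimate effect sizes.
   - Give Holm-adjusted p-values across all primary scores actually analysed, labelled post hoc, and base any statement that an outcome was significant on the adjusted values. If a domain has several subtests, all of them enter the family. Picking one score per domain now would bring back dependence on the results.

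Choosing after the analysis to require every component, and then presenting this as the planned rule, would have the same weakness. Post hoc Holm adjustment discloses and limits the multiplicity but does not restore prespecified error control.

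The cost is a paragraph in the SAP and report, plus adjusted p-values on the second route; no new data are needed. The first route gives up confirmatory wording. The second raises the difference detectable with 80% power at Holm's first step across eight scores from about 0.68 to 0.88 SD (35 per arm, complete data, unadjusted t-test). The planned ANCOVA with covariates would give somewhat different figures, and more scores in the family would raise the threshold further.
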